6.1.1 Efficacy endpoint

Due to the premature stopping of the study, the efficacy endpoints will not be addressed. All available efficacy data will be provided in subjects data listings and described in a descriptive manner in an abbreviated CSR.

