6.1.1.2 Primary endpoint of Phase II

The primary endpoint of Phase II is to determine the magnitude and dynamic range of ^{99m}Tc-rhAnnexin V-128 uptake in disease affected sacro-iliac or lumbar spine joints, in patients with clinical suspicion or confirmed diagnosis of Spondyloarthritis (SpA). SPECT/CT scans will be interpreted and graded by the P.I. and two independent experienced nuclear medicine physicians blinded from clinical data and other imagings modality results. Briefly, ^{99m}Tc-rhAnnexin V-128 uptake compared with background (e.g. physiological liver uptake) should be assessed for each affected area by nuclear medicine physicians using a 4-grade scoring system (0 = none, 1 = mild or present

[REDACTED]

	MDL Modello	Area: 01 Documento: MDL 01.01 Revisione: 0 Data di revisione: 18/04/2013 Pagina: 29 di 85
	Statistical Analysis Plan	
ANNEXIN 03		

but lower than background uptake; 2, moderate or equal to background uptake; 3, intense or greater than background uptake). The assessed uptake will be the score with more adjudications (two or more). In case of discrepancies among the three different readers, an adjudication process based on consensus should be put in place in order to obtain one final outcome for each area.

Imaging procedure result, SUV and uptake intensity grades for SPECT/CT of sacro-iliac and lumbar spine joints will be summarized in descriptive tables; furthermore, concordance between the raters will be assessed with Kendall's W. For both SPECT/CT, two separate analysis will be conducted: one based on values measured 60 min after IP injection and the other on values measured 120 min after IP injection.

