16.2.6 Individual efficacy response data

- Listing 16.2.6.1: Whole Body Planar Imaging – 60 min After IP Injection
- Listing 16.2.6.2: Whole Body Planar Imaging – 120 min After IP Injection
- Listing 16.2.6.3: Abdomen SPECT/CT Imaging – 60 min After IP Injection
- Listing 16.2.6.4: Abdomen SPECT/CT Imaging – 120 min After IP Injection
- Listing 16.2.6.5: Lumbosacral SPECT/CT Imaging – 60 min After IP Injection
- Listing 16.2.6.6: Lumbosacral SPECT/CT Imaging – 120 min After IP Injection
- Listing 16.2.6.7: Sacroiliac SPECT/CT Imaging – 60 min After IP Injection
- Listing 16.2.6.8: Sacroiliac SPECT/CT Imaging – 120 min After IP Injection
- Listing 16.2.6.9: Spot SPECT/CT Imagings – 60 min After IP Injection
- Listing 16.2.6.10: Spot SPECT/CT Imagings – 120 min After IP Injection

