10.2 Listing templates

Listing templates are provided in Appendix 11.1. The listings will be presented in landscape, in a fixed font (Arial) with a minimum size as 8.

The page number of each listing shell (n of N) represent n=page number of the listing and N=total number of pages for that specific listing.

Each listing must be presented in an independent, separate Word file for each ICH heading (e.g. Listings 16.2.9.X combined in one file).

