	MDL Modello	Area: 01 Documento: MDL 01.01 Revisione: 0 Data di revisione: 18/04/2013 Pagina: 62 di 85
	Statistical Analysis Plan	
ANNEXIN 03		

Listing 16.2.6.1: Imaging Results

Subject ID	Region	Time point	Has the imaging been completed?	Reason for not performing the imaging	Date	Time	Has the image been reviewed?	Result	Grade of uptake		
									PI	Reviewer 1	Reviewer 2
03-US-001	Whole Body Planar	60 min	Yes		11/03/2011	10:50	Yes	Positive	0	0	1
		120 min	Yes		11/03/2011	11:50	Yes	Positive	0	0	1
	Spot SPECT/CT: XXXXX	60 min	Yes		11/03/2011	10:50	Yes	Positive	0	0	1
		120 min	Yes		11/03/2011	11:50	Yes	Positive	0	0	1
	Etc...										
03-US-002			Yes		03/03/2011	10:00	Yes		2	3	2
03-US-003			No	XXXXXXX			No				

	MDL Modello	Area: 01 Documento: MDL 01.01 Revisione: 0 Data di revisione: 18/04/2013 Pagina: 63 di 85
	Statistical Analysis Plan	
ANNEXIN 03		

Listing 16.2.7.1/1: All Adverse Events

Subject ID	Event ID	Event description	SOC	PT	LLT	Day of onset [§] (day)	Ongoing?	Duration (days)	TEAE [^]
PAT_PATNUMBER	ID_WEB	AE_NAME	MEDDRA_SOC	MEDDRA_PT	MEDDRA_LLT	[Derived Data]	AE_ONGOING_YN	[Derived Data]	[Derived Data]
03-US-001	XXX	XXXXXXXX	XXXXXX	XXXXXXXX	XXXXXX	YY	■	■	■
03-US-002	XXX	XXXXXXXX	XXXXXX	XXXXXXXX	XXXXXX	YY	■	■	■
03-US-003	XXX	XXXXXXXX	XXXXXX	XXXXXXXX	XXXXXX	YY	■	■	■

Data Source Table: W_PATIENT, W_AE.

SOC: System Organ Class

PT: Preferred Term

LLT: Lowest Level Term Dictionary Name: MedDRA Version: XX.X

[§] Start day of onset in regarding to the annexin injection

[^]TEAE: Treatment Emergent Adverse Event

Note: NA = Not Available

File directory: *path of directory status from study level downwards* /XXXXXX.sas

	MDL Modello	Area: 01 Documento: MDL 01.01 Revisione: 0 Data di revisione: 18/04/2013 Pagina: 64 di 85
	Statistical Analysis Plan	
ANNEXIN 03		

Listing 16.2.7.1/2: All Adverse Events

Subject ID	Event ID	Event description	AE caused premature withdrawal?	SAE	SAE seriousness	Maximal severity	Causal relationship with medication or procedure	Possible cause	Specify other possible cause	TEAE [^]
PAT_PATNUMBE R	ID_WEB	AE_NAME	AE_WITHD_YN	AE_SAE_YN	[Derived Data]	AE_MAXSEV	AE_REL	AE_CAUSE	AE_CAUSE_SP	[Derived Data]
03-US-001	XXX	XXXXXXXX	Yes	Yes	XXXXXX / XXXXX / XX	Grade 2 (Moderate)	Possible	Other	XXXXXXXXXXXX	Yes
03-US-002	XXX	XXXXXXXX	No	No	XXXXXX / XXXXX / XX	Grade 1 (Mild)	Unlikely	Pre-existing/underlying disease	XXXXXXXXXXXX	Yes

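### Does the imaging listing shell leave out SUV and the final uptake grade that the close-out report needs?

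*SAP*

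**What the plan says.** SAP 6.1.1 states that the efficacy endpoints will not be addressed because the study stopped early, and then: "All available efficacy data will be provided in subjects data listings and described in a descriptive manner in an abbreviated CSR". SAP 8 records the closure after five patients and limits the output to listings and a short report.

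SAP 6.1.1.2 still carries the full plan for the Phase II primary endpoint. Scans are "graded by the P.I. and two independent experienced nuclear medicine physicians blinded from clinical data". The grade runs from 0 to 3. On combining the readers it says "The assessed uptake will be the score with more adjudications (two or more", and it sends discrepancies among the three to consensus "in order to obtain one final outcome for each area". For reporting: "Imaging procedure result, SUV and uptake intensity grades for SPECT/CT of sacro-iliac and lumbar spine joints will be summarized in descriptive tables".

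On layout, SAP 10.2 says "Listing templates are provided in Appendix 11.1". The one nuclear-imaging shell there is headed "Listing 16.2.6.1: Imaging Results". Its columns are subject, region, time point, completion, reason, date, time, reviewed, Result, and grades by PI, Reviewer 1 and Reviewer 2. The index in SAP 10.1 instead names ten imaging listings by region and time, for example "Listing 16.2.6.7: Sacroiliac SPECT/CT Imaging – 60 min After IP Injection".

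Protocol 10.9 asks for at least two independent blinded readers, with consensus where they differ.

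**The concern.** With summary tables cancelled, the listings are the main record of the imaging data. Set against 6.1.1.2, the shell seems to omit two things: SUV, and the single grade per area that the section defines as the outcome.

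The primary objective is magnitude and dynamic range of uptake, and Protocol 4 treats the dynamic range as critical for sizing later studies. Grade 3 covers everything above background, so grades alone cannot show magnitude beyond that point. If SUV exists and is not printed, that information would be missing from the listings. If the final grade is not printed, the report text has no listed value to cite.

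There is also a question of record. Protocol 10.9 mentions neither the P.I. as a reader nor a majority vote. SAP 8 does not list them as changes, and the sentence naming the readers leaves it unclear whether the blinding covers the P.I.

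**Working it through.** The plan states no figure to reproduce. The check sets the sections side by side and asks when the final grade can be recovered from what the shell prints.

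**Size of the listing.** Assume all five patients were imaged at both times, with one graded area per region.
- Primary regions: 5 patients × 2 regions × 2 times = 20 lines, carrying 20 × 3 = 60 reader grades.
- With the abdomen, for which SAP 6.1.1.3 also names SUV: 5 × 3 × 2 = 30 lines.

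**Recovering the final grade.** Three readers on a four-point scale give 4³ = 64 patterns:
- unanimous: 4
- two to one: 4 × 3 × 3 = 36
- all different: 4 × 3 × 2 = 24

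Read in order, 6.1.1.2 lets a score given by two or more readers stand and keeps consensus for the rest. The final grade then follows from the printed grades in 4 + 36 = 40 patterns. In the other 24 it is a consensus value that the shell does not show. These are counts of patterns, not expected rates.

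**A rough rate.** The documents give no reader-agreement data. Assume independent readers, each giving the true grade with probability a between 0.6 and 0.8 and otherwise an adjacent grade.
- True grade 1 or 2: P(all different) = 6 × a × ((1−a)/2)² = 1.5a(1−a)². This is 0.144 at a = 0.6, 0.0945 at 0.7 and 0.048 at 0.8.
- True grade 0 or 3: there is only one adjacent grade, so P(all different) = 0.
- Over 20 lines: 0 to 20 × 0.144 = 2.9, that is, 0 to 3 lines.

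Two-to-one splits would be common under the same model, at 44% to 72% of lines. Nothing is lost there, because the majority grade is visible.

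**Is SUV available?** SAP 6.1.1.2 and 6.1.1.3 name SUV only in sentences about descriptive tables, which 6.1.1 and 8 cancel. Protocol 8.5 and SAP 4.3.3.2.1 plan target-to-background ratio and ROI/VOI counts instead, and the protocol never mentions SUV. Nothing shows that SUV was recorded. The listing commitment in 6.1.1 covers available data.

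**Are the shell's columns exhaustive?** No text says so.
- SAP 10.2 governs font, page numbering and files, and 11.1 describes shells filled with example data.
- SAP 11.4 puts time from injection for each imaging assessment into listings or tables, yet the imaging shell has no such column.
- One shell with region and time-point columns stands in for ten indexed listings. Likewise, one vital-signs shell stands in for two.

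**P.I. and majority vote.** Reviewers 1 and 2 differ in 4 × 3 × 4 = 48 of the 64 patterns. The P.I. matches one of them in 24, so the vote decides. The other 24 go to consensus. Protocol 10.9, applied to those two readers alone, would send all 48 to consensus. The vote can therefore matter for a grade. However, three readers satisfy the protocol's minimum of two, Protocol 10 leaves detailed methods to the SAP, and all three grades are printed.

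**The case for a change.** The strongest case for a change is that a programmer works from the shell. This one lacks even the row of database variable names that most other shells carry, so values outside its columns could be missed. No indexed listing is titled for a quantitative measure. The Result column is no substitute for the final grade: its source is not stated, and the mock row shows a positive Result beside grades 0, 0 and 1. The fix would cost a column or two, a footnote and a line in SAP 8.

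Much of this is factually right. The shell and the index do not match, a consensus grade has no column, and SAP 8 does not mention the P.I. reader or the vote. Some of it goes further than the documents allow. MRI results appear in Listing 16.2.4.2/2, and a report describing the efficacy data remains, so this shell is not the only imaging output. The two-to-one case is ambiguous only if the majority sentence is ignored. Adding SUV to every indexed imaging listing would also exceed the plan, since 6.1.1.3 names no SUV for whole body planar images. What stands is that the documentation could be tidier.

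**Conclusion.** No change to the plan is needed. This is a reporting gap that the SAP's own text already covers: 6.1.1 requires available efficacy data to be listed and described, so a recorded SUV, background ratio or consensus grade has to appear whether or not the specimen shell has a column for it. The final grade follows from the printed grades except after three-way disagreement, which affects 0 to 3 of 20 primary-region lines under the assumed 60% to 80% reader accuracy. The SUV gap is real only if SUV was collected, which the documents do not establish.

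The stakes are small. The five patients form the proof-of-concept part, whose criteria SAP 6.1.1.1 leaves to the DMC charter. The final grade belongs to the Phase II endpoint, which is not being addressed. Extra columns, a statement on P.I. blinding or an entry in SAP 8 would document matters better but would alter no estimate, test or conclusion. This rests on reading the majority sentence before the consensus sentence, and on the sponsor keeping the commitment in 6.1.1.

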6.1.1.3 Secondary endpoints

The secondary endpoints of Phase II and the related statistical analyses are:

- a) Endpoint: to determine the clinical utility of ^{99m}Tc -rhAnnexin V-128 SPECT/CT imaging in the identification of chronic osteoarthritic active sites of SpA compared with conventional imaging (MRI), in patients with disease affected sacro-iliac or lumbar spine joints.

Statistical analysis: for quantifying the radioactivity uptake after injection of ^{99m}Tc -rhAnnexin V-128, ROIs will be drawn manually on the earliest images, and the shapes and sizes (i.e. number of pixels) will be kept constant over all subsequent images. Correction for background counts will be performed using an appropriate background region by subtracting the mean counts per pixel in the background region from the mean counts per pixel in each ROI to yield net counts. For each ROI, the geometric mean of net counts, corrected for physical decay, of total anterior and posterior counts will be calculated. In order to compare SPECT/CT scans and MRI scans, diagnostic performances will be evaluated in terms of sensitivity (i.e. true positive rate), specificity (i.e. true negative rate), positive predictive value (i.e. proportion of positive values) and negative predictive value (i.e. proportion of negative values). This analysis will be performed for both region, sacro-iliac and lumbar spine joints. To do this, physical examinations will be necessary to define sites of pain in patients with clinical suspicion or confirmed diagnosis of SpA. When sites of pain will match with abnormalities on diagnostic images, this will be regard as true positive. Furthermore, for all the performed statistics, a two sided 95% C.I. will be computed

[figure not shown]
	MDL Modello	Area: 01 Documento: MDL 01.01 Revisione: 0 Data di revisione: 18/04/2013 Pagina: 30 di 85
	Statistical Analysis Plan	
ANNEXIN 03		

- b) Endpoint: to assess the presence of antibodies against rhAnnexin V-128 at baseline and post-treatment.

Statistical analysis: The determination of antibodies against rhAnnexin V-128 at baseline and post-treatment will be described as present or absent; these data, related to immunogenicity, will be described in contingency tables reporting frequencies and percentages.

- c) Endpoint: to determine the localization pattern and magnitude of focal uptake of ^{99m}Tc-rhAnnexin V-128 within the abdomen in patients with clinical suspicion or confirmed diagnosis of Spondyloarthritis (SpA).

Statistical analysis: Imaging procedure result, SUV and uptake intensity grades for SPECT/CT of abdomen and of spot views, and imaging procedure result and uptake intensity grades for whole body planar imaging will be summarized in descriptive tables; furthermore, concordance between the raters will be assessed with Kendall's W. For each imaging assessment, two separate analysis will be conducted: one based on values measured 60 min after IP injection and the other on values measured 120 min after IP injection

	MDL Modello	Area: 01 Documento: MDL 01.01 Revisione: 0 Data di revisione: 18/04/2013 Pagina: 31 di 85
	Statistical Analysis Plan	
ANNEXIN 03		

6.1.2 Safety endpoint(s)

Safety and tolerability will be primarily evaluated by the incidence of adverse events, clinical laboratory values (hematology, blood chemistry and urinalysis), vital signs (blood pressure and heart rate) and physical examination findings.

All safety data will be included in the data listings and summary tables will be based on the safety population. The statistical analysis of safety data will be mainly descriptive in nature.

Categorical data will be presented as frequencies, percentages and 95% confidence interval if relevant. For continuous data, N, missing, mean, standard deviation, median, quartiles, minimum, maximum and if relevant 95% confidence interval will be presented. Graphs such as box plots, circular diagrams or histograms can also be computed if relevant. Considering the small sample size planned in this study, non-parametric approach will be favored.

6.1.2.1 Adverse events

All original AE/SAE terms will be coded using the Medical Dictionary for Regulatory Activities (MedDRA v.19.0).

Adverse events will be listed on an individual basis, including relationship and severity, LLT, LLT code and verbatim term. Treatment Emergent Adverse Events (TEAEs) and Adverse Drug Reactions will be summarized by System Organ Class (SOC) and Preferred Term (PT). Patients with more than one adverse event within a particular SOC and PT will be counted only once for that SOC and PT reporting the highest level in severity. The incidence of TEAEs and ADRs will also be summarized by severity and relationship to the investigational imaging product. In the case several patients have experienced more than one adverse event, detailed descriptive statistics may also be presented on patients with 2, 3 or more than 3 AEs, if relevant.

Adverse drug reactions (ADRs, i.e. all AEs at least possibly related to the study drug according to the investigator) will be summarised in a similar way to TEAEs. Listings of serious adverse events (SAE), adverse events leading to withdrawal and listings of deaths will also be presented.

Treatment Emergent Adverse Events and Adverse Drug Reactions will be defined as below:

	MDL Modello	Area: 01 Documento: MDL 01.01 Revisione: 0 Data di revisione: 18/04/2013 Pagina: 32 di 85
	Statistical Analysis Plan	
ANNEXIN 03		

- Treatment Emergent Adverse Events: Events that emerge after the ^{99m}Tc-rhAnnexin V-128 injection and up to 30 days after the injection that were absent before it or worsen relative to the pre-treatment state.
- Adverse Drug Reactions: Treatment emergent adverse events possibly or probably related to treatment.

6.1.2.2 Clinical laboratory values

Hematology, blood chemistry, urinalysis and immunogenicity values are recorded at baseline for screening and 30 days post IP administration. Descriptive statistics will be tabulated by measuring time for raw data and changes from baseline; boxplots will be reported, if appropriate. Data listing will be ordered by subject and measuring time. A listing of all the abnormal values (clinically and non-clinically relevant) will be reported.

6.1.2.3 Vital signs and physical examination

Vital signs data are recorded once at screening visit and twice at imaging visit (Day 0), before the injection of ^{99m}Tc-rhAnnexin V-128 and after the last imaging procedure (within 2 hrs after ^{99m}Tc-rhAnnexin V-128 injection). Physical examination data are recorded at screening visit and at Day 30. Descriptive statistics will be tabulated by measuring time for raw data and changes from baseline (screening visit); boxplots will be reported, if appropriate. For day 0, post imaging procedures values will also be compared with pre injection counterparts (i.e. assessed on the same day). If appropriate, comparisons between different measuring times will be performed according to appropriate non-parametric paired inferential statistics. Data listing will be ordered by subject and measuring time.

6.1.3 Multiplicity

Due to the exploratory nature of the study no adjustments will be made for multiplicity.

	MDL Modello	Area: 01 Documento: MDL 01.01 Revisione: 0 Data di revisione: 18/04/2013 Pagina: 33 di 85
	Statistical Analysis Plan	
ANNEXIN 03		

6.1.4 Significance testing and estimation

All statistical tests will be two-sided at the 5% level of significance.

6.1.5 Missing data and outliers

6.1.5.1 Missing data

As stated in the protocol, missing data will not be replaced.

6.1.5.2 Missing or incomplete dates

Incomplete dates due to missing day will be recorded as full dates replacing the missing day with the first day of month (01). Incomplete dates due to missing day and month will be recorded as full dates replacing the missing day and month with the first day of month and first month of the year (01/January). The trial database will record the information about incomplete dates due to missing day or due to missing day and month.

Only the incomplete dates related to date of birth, SpA diagnosis date, medical history (date of diagnosis and end date), concomitant medications (start and end date) and AEs (start and end date) will be replaced according to the above rule.

Calculation, sorting or assignation based on dates, in case of incomplete dates, will be performed using the related full dates defined by the above rule.

In all listings, missing and incomplete dates will be reported as full dates. In all listings will be also reported the information about incomplete dates according to the following coding: missing value = full date, Day = missing day, Day&Month = missing day and month.

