4.3.3.3 Safety assessments

- Physical examination will be conducted at D30.
- Measurement of vital signs (systolic and diastolic blood pressure and heart rate) will be performed 15 minutes before the radiotracer administration and at the end of the last imaging procedure at Day 0.
- Women of childbearing potential must have negative urine pregnancy test before injection of the radiotracer at Day 0.
- All medications taken from 2 weeks prior to the administration date through the end of study are to be recorded as prior and concomitant medications, including therapies for SpA.
- Any adverse events occurring during the course of the study will be reported and recorded in the eCRF. 24 hours after treatment injection (at Day 1), each patient will be called in order to inquire if they experienced signs or symptoms such as edema, rash or have any clinical findings.

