6.1.12 Prior and concomitant therapies

Concomitant therapies will be coded using ATC Drug Dictionary.

Listings will be presented for active substance, ATC code and verbatim text. The listings will be sorted by subject, chronological start date, active substance, ATC code and verbatim text.

A frequency table of the number and percentage of subjects will be provided for concomitant therapies by Anatomical Main Group and Chemical substance for Safety population. Two different tables will report Prior Therapies (the drug therapies taken prior to the ^{99m}Tc-rhAnnexin V-128 injection) and Concomitant Therapies (the drug therapies that started after the ^{99m}Tc-rhAnnexin V-128 injection or that were ongoing at the start of ^{99m}Tc-rhAnnexin V-128 injection).

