	MDL Modello	Area: 01 Documento: MDL 01.01 Revisione: 0 Data di revisione: 18/04/2013 Pagina: 58 di 85
	Statistical Analysis Plan	
ANNEXIN 03		

Listing 16.2.4.4/1: Prior and Concomitant Medications

Subject ID	Medication trade name	ATC description	Start date (day)	Partial date	Ongoing?	End date	Partial date
PAT_PATNUMBE R	CM_NAME	ATC_DESCR	CM_START_DATE	CM_PARTIAL_STA RT_DATE	CM_ONGOING_Y N	CM_END_DATE	CM_PARTIAL_EN D_DATE
03-US-001	XXXXXXXX	XXXXXX	15/08/1990 (-1)	Day	No	14/04/1994	Day
03-US-002	XXXXXXXX	XXXXXX	31/12/2007 (2)	Day&Month	No	15/06/2008	Day&Month
03-US-003	XXXXXXXX	XXXXXX	05/05/2005 (X)		Yes	Resolution date	

	MDL Modello	Area: 01 Documento: MDL 01.01 Revisione: 0 Data di revisione: 18/04/2013 Pagina: 59 di 85
	Statistical Analysis Plan	
ANNEXIN 03		

Listing 16.2.4.4/2: Prior and Concomitant Medications

Subject ID	Medication trade name	Total daily dose	Unit	Specify other unit	Frequency of administration	Specify other frequency	Route of administration	Specify other route
PAT_PATNUMBE R	CM_NAME	CM_DOSE	CM_DOSEU	CM_DOSEU_SP	CM_FREQ	CM_FREQ_SP	CM_ROUTE	CM_ROUTE_SP
03-US-001	XXXXXXXX	3	G		BID		OtherI	XXXXXX
03-US-002	XXXXXXXX	3	Other	XXXXXX	TID		Intramuscular	
03-US-003	XXXXXXXX	12	Mg		Other	XXXXXX	Subcutaneous	

	MDL Modello	Area: 01 Documento: MDL 01.01 Revisione: 0 Data di revisione: 18/04/2013 Pagina: 60 di 85
	Statistical Analysis Plan	
ANNEXIN 03		

Listing 16.2.5.1/1: Study Drug Administration and Extent of Subject Exposure

Subject ID	Has the injection been performed?	Reason for not performing the injection	Injection date	Injection time	Batch of kit	Batch of ^{99m} Tc generator
PAT_PATNUMBER	ANN_YN	ANN_YN_SP	ANN_DATE	ANN_TIME	ANN_KIT	ANN_GEN
03-US-001	Yes		11/03/2011	10:50	09101-110631	09101-110631
03-US-002	Yes		03/03/2011	10:00	09101-110981	09101-110981
03-US-003	No	XXXXXXX				

	MDL Modello	Area: 01 Documento: MDL 01.01 Revisione: 0 Data di revisione: 18/04/2013 Pagina: 61 di 85
	Statistical Analysis Plan	
ANNEXIN 03		

Listing 16.2.5.1/2: Study Drug Administration and Extent of Subject Exposure

Subject ID	Has the injection been performed?	Reason for not performing the injection	Radiochemical purity	Pre injection total dose in the syringe	Post injection residual dose in the syringe	Actual dose injected	Volume of solution
PAT_PATNUMBER	ANN_YN	ANN_YN_SP	ANN_TEST1	ANN_TEST2_PRE	ANN_TEST2_POST	ANN_TEST2_EFF	ANN_TEST2_VOL
03-US-001	Yes		98.7%	123	123	123	123
03-US-002	Yes		99.1%	456	456	456	456
03-US-003	No	XXXXXXX					

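### Partial medication stop dates are set to the earliest possible day, so a drug still in use at the tracer injection can be dated as stopped before the scan

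*SAP*

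**What the plan says.** SAP 6.1.5.2 (Missing or incomplete dates) has one replacement rule: a missing day becomes the 1st of the month, and a missing day and month become 1 January. The scope sentence covers both ends of a medication record: "concomitant medications (start and end date) and AEs (start and end date) will be replaced according to the above rule".

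Two further sentences make the replaced date operative. "Calculation, sorting or assignation based on dates, in case of incomplete dates, will be performed using the related full dates", and "In all listings, missing and incomplete dates will be reported as full dates". The section also asks listings to carry a code for which part of the date was missing.

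SAP 6.1.12 (Prior and concomitant therapies) separates two groups by date. The concomitant definition opens "Concomitant Therapies (the drug therapies that started after the" injection and adds drugs ongoing when the injection is given. Prior therapies are those taken before it. Each group was to have its own table.

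On collection, SAP 4.3.3.3 states: "All medications taken from 2 weeks prior to the administration date through the end of study are to be recorded".

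SAP section 8 records that the study closed after the first 5 patients and that only subject data listings will be produced. The relevant template in SAP 11.1 is "Listing 16.2.4.4/1: Prior and Concomitant Medications". It has a start date with a day relative to injection in brackets, an end date, a partial-date column beside each, and an ongoing column.

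**The concern.** Moving a start date to the earliest day and moving a stop date to the earliest day have opposite effects on exposure. The first lengthens the recorded period of use and the second shortens it. Applied to stop dates, the rule removes exposure that may have covered the injection.

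The design makes this more than theoretical. Patients are scanned shortly before a change of NSAID or a change or start of DMARD (Protocol 5.1, SAP 4.2 and 4.2.1.1), so stops soon after the scan, often in the same month, are to be expected. What is at stake is the record of which anti-inflammatory drugs a patient was taking when the images were acquired.

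Medications also lack a safeguard that adverse events have. SAP 11.4 reports adverse event duration and delay of onset as inequalities when a date is partial. It contains nothing comparable for medications.

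**Working it through.** The documents give no figure on this point, so there is none to reproduce. The check applies the rule to examples and then counts cases.

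**Examples** (injection 10 June, non-leap year)

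| True stop | Recorded as | Replaced by | Relative to injection | Result under 6.1.12 |
|---|---|---|---|---|
| 24 June | June, day missing | 1 June | 9 days before | prior only |
| 24 June | year only | 1 January | 160 days before | prior only |
| 5 July | July, day missing | 1 July | 21 days after | stays concomitant |

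A drug with a full start date of 5 June and a stop recorded only as June would be given an end of 1 June, before its own start.

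**Same-month model.** Assumption: injection day d and true stop or start day s are independent and uniform on days 1 to 30 of the same month, giving 30 × 30 = 900 pairs.

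- Stop on or after the injection day but dated before it (s ≥ d, d > 1): 29 + 28 + … + 1 = 435, and 435/900 = 48%.
- Start after the injection but dated before it (s > d, d > 1): 28 + 27 + … + 0 = 406, and 406/900 = 45%.
- Replaced stop date more than 14 days before injection (d − 1 > 14, so d from 16 to 30): 15/30 = 50%. Such a stop falls before the two-week recording period in SAP 4.3.3.3 begins.

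**Second model, as a range.** Take every injection date in a 365-day year and true stops spread evenly over 1 to W days after injection, so that every drug is in use at the scan. The share dated as stopped before injection is:

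| W (days) | Day missing | Day and month missing |
|---|---|---|
| 7 | 83.6% | 98.6% |
| 14 | 72.1% | 97.7% |
| 30 | 45.8% | 95.5% |
| 33 | 41.7% | 95.1% |

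The 33-day limit is the upper end of the Day 30 visit window in SAP 6.1.14. All these figures are shares of partial dates; the documents do not say how many dates are partial.

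**Effect of using the latest possible stop date.** In the second model the error falls to 0% for every W. A cap at the last visit does not alter this, provided that visit is not before injection. The opposite error appears: in the same-month model, stops before injection that would be shown as in use are P(s < d) = 435/900 = 48%. Among drugs truly stopped 1 to 14 days before injection, 75% (day missing) or 98% (day and month missing) would count as ongoing.

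**The case against.** The best defence is that little of this reaches the output. SAP section 8 leaves listings only, so the two tables of 6.1.12 are not produced, and Listing 16.2.4.4 combines prior and concomitant drugs without a column for the class. Each replaced date is flagged, so a reader who sees 1 June coded as day missing knows that only June was recorded. No planned analysis uses these dates: SAP 6.1.1 says efficacy endpoints will not be addressed, and 6.1.19 has no covariates or subgroups. Drugs marked ongoing have no stop date to replace, and a month-only stop in a later month stays after the injection.

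All of that stands, and it rules out three stronger inferences a reader might draw.

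- That drugs disappear from the concomitant therapies in the report. This follows from the 6.1.12 rule and tables as written, but those tables are cancelled.
- That drugs in use at injection vanish from the safety record. They would still count as prior therapy and still appear in the listing.
- That new therapies begun after the scan are lost from the concomitant group. A drug dated to the 1st that continues past injection still counts as ongoing. The 45% is a wrong displayed start date, not a lost drug.

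The defence does not remove the defect. The flag shows that a date was replaced, but not whether the drug was in use at the scan. The listing template also prints a relative day on start dates flagged as partial, which gives an order relative to injection that the data may not support.

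**Conclusion.** The rule is wrong as written for medication stop dates, and nothing elsewhere in the SAP corrects it. It affects only drugs whose stop is recorded as the injection month without a day (injection not on the 1st) or as the injection year without a month.

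In the planned output the effect is a false, flagged stop date and, for partial starts, a false relative day in a five-patient listing. Misclassification as prior only is a property of 6.1.12 as written and would matter if its tables were produced.

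The 48% rests on uniform, independent days within one 30-day month. The second model gives 42% to 84% with the day missing, depending on how soon after the scan drugs are stopped. Neither says how often stop dates are partial. Severity: minor.

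**What to change.** Four changes to the SAP:

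1. In 6.1.5.2, replace partial medication end dates with the latest possible date: the last day of the month, or 31 December if the month is also missing. Cap it at the last study visit.
2. In 6.1.12, class a drug as concomitant unless the recorded parts of its dates prove that it stopped before injection.
3. In Listing 16.2.4.4, print partial dates as recorded, and give no relative day where the order relative to injection is unknown. This needs an exception to the full-date instruction in 6.1.5.2.
4. Do not fill in start dates from the planned-treatment category in the disease assessment listing. That would assume the design was followed and could hide a therapy begun before the scan.

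The cost is a few lines of text and code. The statistical cost is the opposite error shown above. Overcounting is the cautious direction for a record of concomitant use, but not for interpreting uptake. Drugs whose order relative to injection is unknown should therefore stay flagged as uncertain.
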